8.2 Randomization, blinding and treatment allocation

Patient will be randomized between group 1 (deep NMB) or group 2 (standard care) just prior to surgery by an independent research nurse. Randomization will be performed using a dedicated, password protected website. The randomization sequence is generated by a dedicated computer randomization software; Castor (Castor EDC, CIWIT B.V., www.castoredc.com), stratified per center and BUPA category (MAJOR, MAJOR PLUS or COMPLEX MAJOR). To ensure a balanced distribution block, randomization will be used with 2 and 4 cases per block.

Blinding:

During every procedure, an unblinded researcher will be present to ensure adherence to the study protocol. Specifically, he or she will be responsible for maintaining the desired level of NMB. The researcher will not be involved in scoring of the Classic events (primary outcome). Classic scorings will be done by the attending anesthesiologist and surgeon who will be blinded.

To avoid deblinding of the surgical team in the standard NMB group (by noting the absence of a rocuronium perfusion), a syringe pump with NaCl 0.9% will substitute the rocuronium infusion.

Postoperative care nurses and the investigator assessing postoperative endpoints are blinded to group allocation. Additionally, data analysis will be performed by blinded researchers.

8.3 Study procedures

Informed consent procedure

Patients will be screened for eligibility on the routine preoperative visit at the anesthesia outpatient department. Should a patient be eligible, than he or she will be contacted by one of the researchers by phone to receive oral and written information about the study. This contact will take place at least 2 weeks prior to the surgical procedure. If the patient is willing to participate, written consent will be obtained

Preoperative procedures

After informed consent has been obtained, baseline QoR-40 and SF36 questionnaires will be taken prior to surgery and randomization.

Perioperative procedures

Anesthesia procedures: Anesthesia procedures will follow local protocol on all aspects, except for

the neuromuscular block. Standard anesthesia iv access and standard monitoring according to local institutional protocol will be applied. General anesthesia will be induced and maintained with propofol or sevoflurane or desflurane. Intraoperative antinociceptive treatment will be with sufentanil, fentanyl or remifentanil. The choice regarding the type of hypnotic and opioid is upon the discretion of the attending anesthesiologist and is not influenced by this study. Hypnotic depth of all patients will be routinely monitored with bispectral index monitoring (BIS module, Philips, Eindhoven, The Netherlands) or entropy assessment to assess the level of hypnosis. The target level of the BIS is 50 +/- 5 during the procedure, and propofol dosage or end-tidal sevoflurane/desflurane will be steered to maintain the target BIS level to avoid under- or overdosing of the hypnotic agent.

Postoperative pain relief will be ensured with morphine, or equivalent (eg. Piritramide or methadone), and NSAIDs (eg. Diclofenac 50 - 75 mg) or metamizole 1g, and acetaminophen 1g. Lidocaine iv, magnesium, β -blocking agents, and/or loco-regional infiltration / techniques are not allowed.

Ventilation: will be adjusted to maintain end-tidal pCO₂ of 4.5 to 5.5 kPa.

Postoperative pain relief. Pain relief at the PACU is left to at discretion of the attending anesthesiologists. All analgesics that are administered will be recorded in the e-CRF

Neuromuscular management

All patients will receive neuromuscular monitoring according to international guidelines for neuromuscular monitoring in research.[15] Neuromuscular monitoring will exclusively be applied at the m. adductor pollicis of one of the free moving thumbs. The following devices are allowed in this study: TOF-scan, Idmed, France, CE 0459 TOF-Watch, Organon, Ireland, CE 0543; or electromyography; GE NMT, GE-healthcare, Finland, CE 0537 .

All monitors will be applied in accordance with the guidelines of the manufacturer, including any baseline and calibration procedures; these will take place after the patient has been put under general anesthesia, but before the administration of any NMBA. Baseline TOF ratio will be noted in the CRF. All monitor types can be used interchangeably in practice of this study. Patients may only be extubated when the TOF ratio is at least 0.9.

Surgical procedures: All laparoscopic procedures will exclusively be performed at standard insufflation pressures (IAP 12 mmHg). After insufflation, intra- abdominal volume will be recorded. This provides an indirect measure of abdominal wall compliance and workspace.

Intra operative scoring procedures

Intra operative adverse events

Intra operative adverse events will be scored using the CLASSIC score (see table 2). This score has recently been developed and validated in a Delphi study (NCT03009929). Scoring of the CLASSIC scale

will be done by the blinded surgeon and blinded attending anesthesiologist (based on consensus) at the end of every procedure. Notably, the unblinded researcher on the OR is NOT involved in the scoring. CLASSIC classification is only applicable for events that have occurred *during* the procedure, any adverse event at PACU and beyond will be scored using Clavien Dindo scale (see table 6).

All surgeons will be trained prior to inclusion to objectively score CLASSIC grades consistently over the different centers. This will be done by a group of investigators that will form a blinded adjudication committee (BAC) that will review each case based on the operative report. The first two to three cases in each center will be attended by the BAC to evaluate whether the surgeons are able to score reliably after the initial training phase. Furthermore, interim evaluation of consistent reporting of the primary outcome will be performed by the BAC after N=10, N=20, N=50, and N=100 cases to check for discrepancies. Further training of surgeons after interim evaluation moments may be warranted

Intraoperative surgical conditions

Surgical working conditions will be scored by the blinded surgeon at 15 minutes intervals during the procedure, using the validated Leiden surgical rating scale (see table 3)[16].

Surgeons involved in the study will be trained in L-SRS scoring prior to study start by the local sub-PI

Table 3. L-SRS classification in laparoscopic surgery[6, 17].

1	Extremely poor conditions: The surgeon is unable to work due to coughing or due to the inability to obtain a visible laparoscopic field because of inadequate muscle relaxation. Additional muscle relaxants are given.
2	Poor conditions: There is a visible laparoscopic field but the surgeon is severely hampered by inadequate muscle relaxation with continuous muscle contractions and/or movements with the hazard of tissue damage. Additional muscle relaxants are given.
3	Acceptable conditions: There is a wide visible laparoscopic field but muscle contractions and/or movements occur regularly causing some interference with the surgeon's work. There is the need for additional muscle relaxants to prevent deterioration.
4	Good conditions: There is a wide laparoscopic working field with sporadic muscle contractions and/or movements. There is no immediate need for additional muscle relaxants unless there is the fear for deterioration.
5	Optimal conditions: There is a wide visible laparoscopic working field without any movement or contractions. There is no need for additional muscle relaxants.

In case of suboptimal surgical working conditions (deterioration of the L-SRS) or an adverse event CLASSIC ≥ 2 , the following measures may be taken (and will be recorded):

1. Administration of rocuronium: 10 mg (repeated on request)
2. Administration of propofol 20-50 mg

3. Additional bolus of opioids (remifentanil, sufentanil, fentanyl)
4. Increasing the intra-abdominal pressure (with a maximum of 16 mmHg)

Immediate postoperative measurements

These postoperative measurements will be recorded by an independent and blinded nurse/researcher at the post anesthesia care unit (PACU). The measurements include:

At 15 minutes intervals

Oxygen saturation and use of any supplemental oxygen

Heart rate and blood pressure

Pain: using numeric rating scale (NRS: 0 no pain to 10 worst pain imaginable)

Sedation scores: using ramsey sedation score (see table 4)

Other variables recorded:

Medication use, including analgesic consumption

Time until discharge readiness: Aldrete score ≥ 9 (see table 5) and NRS < 5

Adverse events at the PACU and beyond will be recorded using the Clavien Dindo scale (see table 6).

These events will be scored by a blinded researcher.

Table 4. Ramsay sedation score.[18, 19]

Score	Response
1	Awake and anxious, agitated, or restless
2	Awake, cooperative, accepting ventilation, oriented, or tranquil
3	Awake, responds only to commands
4	Asleep, brisk response to light, glabella tap, or loud noise
5	Asleep, sluggish response to light, glabella tap, or loud noise
6	Asleep, no response to light, glabella tap, or loud noise

Table 5. Aldrete score[20]

Activity	Respiration	Circulation	Consciousness	Oxygen Saturation
2: Moves all extremities voluntarily/ on command	2: Breaths deeply and coughs freely.	2: BP + 20 mmHg of preanesthetic level	2: Fully awake	2: $\text{SpO}^2 > 92\%$ on room air
1: Moves 2 extremities	1: Dyspnoeic, shallow or limited breathing	1: BP + 20-50 mmHg of preanesthetic level	1: Arousalable on calling	1: Supplemental O^2 required to maintain $\text{SpO}^2 > 90\%$

0: Unable to move extremities	0: Apnoeic	0: BP +50 mmHg of preanesthetic level	0: Not responding	0: SpO ² <90% with O ² supplementation
-------------------------------	------------	---------------------------------------	-------------------	--

Table 6. Clavien-Dindo Classification.[21]

Grade I	Any deviation from the normal postoperative course without the need for pharmacological treatment or surgical, endoscopic and radiological intervention. Allowed therapeutic regimens are: drugs as antiemetics, antipyretics, analgetics, diuretics and electrolytes and physiotherapy. This grade also includes wound infections opened at the bedside.
Grade II	Requiring pharmacological treatment with drugs other than such allowed for grade I complications. Blood transfusions and total parenteral nutrition are also included
Grade III	Requiring surgical, endoscopic or radiological intervention IIIa Intervention not under general anaesthesia IIIb Intervention under general anaesthesia
Grade IV	Life-threatening complication (including CNS complications)‡ requiring IC/ICU IVa Single organ dysfunction (incl. dialysis) IVb Multi organ dysfunction
Grade V	Death of a patient
Suffix 'd'	If the patient suffers from a complication at the time of discharge, the suffix 'd' (for 'disability') is added to the respective grade of complication.

‡ brain haemorrhage, ischaemic stroke, subarachnoidal bleeding, but excluding transient ischaemic attacks (TIA); IC: Intermediate care; ICU: Intensive care unit

Other postoperative measurements

Pain scores (NRS) at movement (and rest) three times daily at the ward until discharge or to a maximum of 72 hours, which will be extracted from the patient clinical charts.

Adverse events on the ward will be evaluated daily at hospitalization until discharge by a blinded researcher using the Clavien Dindo scale.

The quality of recovery score (QOR-40 questionnaire, appendix 1)[22] are filled in by the patient at day 1 and 2 after surgery.

30 days after surgery, a blinded researcher will evaluate any unplanned readmissions. In addition, patients will be contacted whether or not they have been readmitted in this period in any other hospital.

Also the SF36[23] questionnaire will be taken during this contact.

Additionally, the Comprehensive Complication Index (<https://www.assessurgery.com/>) will be used to grade postoperative complications [24]

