8.1.1 Secondary study parameters/endpoints

To study the effect of deep neuromuscular block as compared to standard neuromuscular block on:

- Surgical working conditions (L-SRS, Table 3)
- 30-day post-operative complications (Clavien-Dindo, Table 6)
- 30-day post-operative complications according to the Comprehensive Complication Index
- 30-day unplanned readmission rates
- Quality of recovery at post-operative day 1, 2 and 30 after laparoscopic surgery.
 - Quality-of-recovery (QoR-40 at postoperative day 1 and 2; Aldrete score (Table 5) at the PACU)
 - Quality-of-life at postoperative day 30 (SF36, Appendix 2)

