9.2 AEs, SAEs and SUSARs

9.2.1 Adverse events (AEs)

Adverse events are defined as any undesirable experience occurring to a subject during the study, whether or not considered related to the trial procedure. All adverse events reported spontaneously by the subject or observed by the investigator or his staff will be recorded, only if judged to be substantial deviating from expected standard

clinical course. This includes severe adverse events that influence postoperative recovery or clinical outcome.

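### The 30-day Clavien-Dindo and Comprehensive Complication Index endpoints have no described procedure for finding complications after discharge that do not lead to readmission

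*Combined protocol and SAP*

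**What the plan says.** Section 8.1.1 lists "30-day post-operative complications (Clavien-Dindo, Table 6") and, separately, "30-day post-operative complications according to the Comprehensive Complication Index". Section 2 has the same two endpoints and makes fewer 30-day complications a secondary hypothesis. Unplanned readmission within 30 days is its own endpoint.

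Section 8.3 describes collection. Events at the PACU are scored by a blinded researcher. After that: "Adverse events on the ward will be evaluated daily at hospitalization until discharge by a blinded researcher using the Clavien Dindo scale". For day 30 it lists three things:

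- Readmissions in general: "30 days after surgery, a blinded researcher will evaluate any unplanned readmissions"
- Readmissions elsewhere: "patients will be contacted whether or not they have been readmitted in this period in any other hospital"
- Quality of life: "Also the SF36[23] questionnaire will be taken during this contact"

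The CCI "will be used to grade postoperative complications [24"], with no time point or data source of its own.

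Three other places bear on events after discharge. Section 8.3 says twice that events from the PACU onwards are scored on the Clavien-Dindo scale, without an end date. Section 9.2.2 follows subjects for AEs and SAEs until the final study procedures. Section 9.2.1 limits AE recording to events reported spontaneously or observed by staff, and "only if judged to be substantial deviating from expected standard" clinical course. Section 10.2 tests secondary outcomes at p < 0.01.

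**The concern.** The endpoint window is 30 days, but the last described step that looks for complications as such is the final ward day. Table 6 counts any deviation from the normal course as grade I, and drug treatment beyond the grade I list as grade II. A wound infection treated by a general practitioner in week two would count under that table. It need not lead to readmission, and nothing in 8.3 asks about it.

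Two things are at stake. First, both endpoints can be under-counted, which costs power at a threshold that is already strict. Second, if patients in one arm left hospital earlier, their events would be under daily observation for less time, and that arm could look better without having fewer complications. The CCI summarises graded complications, so it inherits whatever the grading misses.

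**Working it through.** **1. Window against collection**

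| Period | Described procedure (8.3) | Looks for complications in general? |
|---|---|---|
| PACU | Clavien-Dindo scoring, blinded | Yes |
| Ward, to discharge | Daily Clavien-Dindo evaluation, blinded | Yes |
| Discharge to day 30 | None specific; spontaneous AE reporting under 9.2.1 | No |
| Day 30 | Unplanned readmissions, readmission elsewhere, SF-36 | Readmissions only |

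**2. The plan's own sample size (section 4.4)**

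Inputs: 20% against 12% (a 40% relative reduction), two-sided alpha 5% (two-sided is assumed), power 90%, mean rate 0.16.

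n = [1.960 × √(2 × 0.16 × 0.84) + 1.282 × √(0.20 × 0.80 + 0.12 × 0.88)]² / 0.08² = 439.2 per arm.

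The plan states 439. With its dropout allowance, 878 × 1.05 = 921.9, so 922. The figure reproduces. It concerns the primary endpoint and does not change with this point.

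**3. Illustration: equal capture in both arms**

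The documents give no 30-day complication rate and no share arising after discharge. Assumptions: 439 per arm; each patient either has a complication or does not; true 40% relative reduction; a fraction s of events captured in each arm; two-sided alpha 0.01 (critical value 2.576).

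Observed rates are a = s × p in the control arm and b = s × 0.6p in the deep-block arm. With m = (a + b)/2,

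power = Φ{ [(a − b) − 2.576 × SE0] / SE1 }, where SE0 = √(2m(1 − m)/439) and SE1 = √((a(1 − a) + b(1 − b))/439).

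Worked case, p = 20%:

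- s = 1: a = 0.20, b = 0.12, SE0 = 0.0247, SE1 = 0.0246. The argument is 0.66, so power is 75%.
- s = 0.8: a = 0.16, b = 0.096, SE0 = 0.0225, SE1 = 0.0224. The argument is 0.26, so power is 60%.

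| True control rate | All captured | 80% captured | 60% captured |
|---|---|---|---|
| 15% | 56% | 44% | 30% |
| 20% | 75% | 60% | 44% |
| 30% | 95% | 85% | 68% |

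**4. Illustration: unequal capture, no true effect**

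This applies only if length of stay differs between arms. Assume the same true rate in both arms and capture of 70% against 60%. The apparent risk ratio is 0.60/0.70 = 0.86. The rejection probability uses the same formula with both tails; with equal capture it would be 1%.

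| True rate, both arms | Apparent rates | Rejection at 0.01 |
|---|---|---|
| 10% | 7.0% vs 6.0% | 2.5% |
| 15% | 10.5% vs 9.0% | 3.4% |
| 20% | 14.0% vs 12.0% | 4.5% |
| 30% | 21.0% vs 18.0% | 7.3% |

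A smaller gap does less: 70% against 65% capture at a true rate of 30% gives 2.2%.

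**The case against.** The strongest reply is that the plan does not confine scoring to the hospital stay. The sentence ending at discharge is about ward rounds, which must end there. Section 8.3 elsewhere applies Clavien-Dindo from the PACU onwards with no stop date, the endpoints are labelled 30-day, and 9.2.2 carries AE follow-up to the final study procedures, the last of which appears to be the day-30 contact. Figure 1 is not shown and its legend names the CCI, so it may place the CCI at day 30. Section 9.2.1 is also a safety-reporting rule and need not govern endpoint scoring.

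Most of this stands as a limit on the claim. A reader might infer that complications are collected only until discharge and that later ones are lost. The documents do not support that: an event reported spontaneously, or one leading to readmission, could still be found and graded. What the reply does not supply is a procedure. Naming a scale does not find events, the safety route depends on spontaneous report or observation and filters out minor deviations, and a box in a flowchart would not say who asks what.

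A reader might also infer that the comparison is biased towards the arm that goes home sooner. No passage predicts a difference in length of stay; the hypothesis of better early recovery is not a hypothesis of earlier discharge. Assessors are blinded, and duration of admission is recorded, so a difference would be visible.

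Finally, the trial was not sized for these outcomes, the plan never dichotomises Clavien-Dindo, and the CCI is an index. The power figures therefore show direction and rough scale only.

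**Conclusion.** The point holds in a limited form, with moderate confidence. The 30-day scope of the two endpoints is stated, but no procedure is described for finding complications between discharge and day 30 unless they lead to readmission. Such complications can be missed, and both endpoints under-counted.

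If capture is equal between arms, the cost is power. In the illustration, missing one event in five costs roughly 10 to 14 percentage points across control rates of 15% to 30% (for example 95 − 85 = 10 and 75 − 60 = 15 from the rounded table; 74.6 − 60.4 = 14.2 before rounding). False-positive inflation, about 2.5% to 7% against a nominal 1% under the assumed 70% and 60% capture, is conditional on a difference in length of stay and is a risk to guard against, not an expected result. All these figures rest on assumed complication rates, capture fractions and a binary outcome. Only secondary endpoints are affected. The change should be made because it is cheap and because events not asked about at day 30 are hard to recover later.

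**What to change.** In section 8.3, extend the existing day-30 contact. The blinded researcher asks every patient a short structured list of complications and treatments since discharge (general practitioner, outpatient clinic, emergency department, readmission), checks the hospital record, and grades all events to day 30 on the Clavien-Dindo scale. State that the CCI is computed from that full list.

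If this is not done, relabel both endpoints in sections 2 and 8.1.1 as in-hospital complications plus those found at readmission.

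The cost is a few more questions in a contact that already takes place, one eCRF page and the protocol wording. No extra visit is needed. The small downside is some reliance on patient recall, which the record check only partly offsets.

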8.4 Withdrawal of individual subjects

Subjects can leave the study at any time for any reason if they wish to do so without any consequences. The investigator can decide to withdraw a subject from the study for urgent medical reasons such as anaphylaxis or unanticipated difficult airway at induction of anesthesia.

8.4.1 Specific criteria for withdrawal

Not applicable in this study

8.5 Replacement of individual subjects after withdrawal

Patients who are not randomized (the surgery is cancelled due to logistic or patient factors) are replaced by new subjects. Patients that underwent surgery will not be replaced.

8.6 Follow-up of subjects withdrawn from treatment

Patients who are withdrawn (conversion to deep NMB) by their physician will be subjected to follow up according to the intention to treat principle. When a patient withdraws their consent they will not be subjected to follow-up.

Patient that met the drop-out criteria stated in paragraph 4.4 will not reach the studies primary outcome.

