4.4 Sample size calculation

Preliminary data of the CLASSIC validation study as confidentially provided by dr. [name] (principle investigator; NCT03009929) confirm that the incidence of GRADE ≥ 2 iAEs (Table 2) is 20% for BUPA categories (unpublished data).

Table 2. Adapted version of the CLASSIC classification for intra-operative adverse events (*with permission of dr. [name] (principle investigator of the CLASSIC validation study; NCT03009929).*

Grade 0	No deviation from the ideal intraoperative course
Grade 1	Any deviation from the ideal intraoperative course without the need for any additional treatment or intervention; patient asymptomatic or mild symptoms
Grade 2	Any deviation from the ideal intraoperative course with the need for any additional minor treatment or intervention; patient with moderate symptoms, not life-threatening and not leading to permanent disability
Grade 3	Any deviation from the ideal intraoperative course with the need for any additional moderate treatment or intervention; patient with severe symptoms, potentially life-threatening and/or potentially leading to permanent disability
Grade 4	Any deviation from the ideal intraoperative course with the need for any additional major treatment or intervention; patient with life-threatening symptoms and/or leading to permanent disability
Grade 5	Any deviation from the ideal intraoperative course with intraoperative death of the patient

The following events are not defined as intraoperative complications: sequelae, failures of cure, events related to the underlying disease, wrong-site or wrong-patient surgery or errors in indication

- To date, the minimal clinically important difference (MCID) for intra-operative adverse events according to the CLASSIC classification has not been published. We consider a relative reduction in intra-operative adverse events, CLASSIC grade ≥ 2 , of 40% a clinically relevant difference. As de-

scribed above the reported average rate of grade 2 intra-operative Adverse Events (iAEs) is 20%.

- With an alpha of 5% and beta of 90%, 439 patients are required in each arm of the study (in total 878 patients).
 - Assuming a 5% rate of drop-out a total of 922 patients should be randomized 1:1 in this study. Reasons for drop-out are:
 - conversion to open surgery within the first 20 minutes of the procedure due to unforeseen adhesions, tumor progression, (peritoneal) metastases or other diagnosis

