 - pre-incision alteration of surgical plan to laparotomy instead of laparoscopy after patient randomization to deep NMB or standard-of-care group
 - patient safety concerns at induction of anesthesia, e.g. anaphylaxis at induction of anesthesia or unanticipated difficult airway
 - Patients with a conversion to deep NMB due to intra-operative adverse events will not be excluded.

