5. TREATMENT OF SUBJECTS

There are no specific study-related pre-study requirements. On the day of surgery, patients will be randomized between the two treatment groups. Anesthesia and postoperative care follow routine local protocol, apart from neuromuscular management. Neuromuscular management during surgery depends on the treatment allocation; patients will be randomized between one of the following groups:

Group 1 (experimental): Deep neuromuscular block.

- Muscle relaxation with rocuronium (Esmeron, MSD BV), target depth: post-tetanic-count of 1-2 twitches from start of surgery until the end
- Induction dose rocuronium: 0.6 – 1.0 mg/kg, aimed at PTC 1-2 at surgery start
- Maintenance: continuous infusion of rocuronium at 0.2-0.6 mg/kg/hr, titrated to maintain PTC 1-2
- Reversal of NMB with sugammadex 4 mg/kg at the end of surgery

Group 2 (comparator): standard care

- Muscle relaxation with rocuronium (Esmeron, MSD BV), target depth: train-of-four count of > 0 twitches from start of surgery until the end.
- Induction dose rocuronium: 0.3-0.6 mg/kg, aimed at a TOF count of > 0 twitches at surgery start
- Repeated doses of rocuronium 10 mg on request by the surgeon only
- Reversal of NMB with sugammadex 2 mg/kg at the end of surgery, when TOF ratio < 0.9 at surgery end.

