8. METHODS

8.1 Study parameters/endpoints

Main study parameter/endpoint

Incidence of intra-operative adverse events during laparoscopic surgery (CLASSIC grade ≥ 2 , Table 2) in both groups

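### Sections 4.4 and 8.6 appear to take about 44 of 922 patients out of the primary test after randomisation, two of the routes can follow arm-specific treatment, and no analysis set is named

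*Combined protocol and SAP*

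**What the plan says.** Section 8.2 places randomisation immediately before the operation. Section 4.4 sizes the trial at 439 per arm (878) and then adds an allowance: "Assuming a 5% rate of drop-out a total of 922 patients should be randomized 1:1 in this study". It names three routes out of the study:

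- Once surgery is under way, "conversion to open surgery within the first 20 minutes of the procedure due to unforeseen adhesions, tumor progression, (peritoneal) metastases or other diagnosis".
- Before the first cut, a switch from a laparoscopic to an open operation in a patient who already has an allocation.
- At the start of anaesthesia, "patient safety concerns at induction of anesthesia, e.g. anaphylaxis at induction of anesthesia or unanticipated difficult airway".

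Section 8.6 then says of these patients: "Patient that met the drop-out criteria stated in paragraph 4.4 will not reach the studies primary outcome". The same section applies intention to treat to patients converted to deep block, and 4.4 says those patients stay in. Neither section extends the principle to the three drop-out reasons. Section 10.1 specifies a chi-square test but no analysis set, no rule for patients without a score and no sensitivity analysis.

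Two further provisions matter. Section 5 sets different induction regimens by arm: group 1 is "aimed at PTC 1-2 at surgery start", while group 2 has "Induction dose rocuronium: 0.3-0.6 mg/kg, aimed at a TOF count of > 0 twitches at surgery start". Section 8.4 leaves withdrawal for urgent medical reasons, including events at induction, to the investigator.

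**The concern.** Randomisation makes the arms comparable only for the patients who were randomised. If some leave the primary comparison afterwards, for reasons that may depend on the allocated treatment and on the outcome, the comparison is no longer protected. Two of the three routes can operate after arm-specific treatment has begun.

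- **Early conversion.** It occurs during the operation, under the allocated block. The listed causes are mostly anatomical or disease-related, but the list ends with an unspecified other diagnosis. A conversion may itself be, or may follow, an event of CLASSIC grade 2 or higher, so dropping the patient may drop a primary-outcome event.
- **Safety concerns at induction.** The criterion is given by examples only, and withdrawal is discretionary. Section 8.4 does not say whether the deciding investigator is blinded. Section 8.3 shows that rocuronium is given after general anaesthesia has started. An induction event before the first dose therefore cannot be due to arm-specific dosing, while one after it can. Section 4.4 does not separate the two.

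A change to laparotomy before incision is the route least likely to depend on arm.

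At stake is the only primary test. An event in a patient who drops out would leave an endpoint meant to count such events, although it may still appear in the adverse event reports.

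**Working it through.** **1. Reproduce the plan's figures.** Inputs from 4.4: 20% in the standard arm, a 40% relative reduction (so 12%), alpha 5% (two-sided assumed) and 90% power (printed as beta).

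n per arm = [1.960·√(2·0.16·0.84) + 1.282·√(0.20·0.80 + 0.12·0.88)]² / 0.08² = 439.2. The plan states 439, and power at 439 per arm is 90.0%.

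Drop-out: 878 × 1.05 = 921.9, so 922. Then 922 − 878 = 44, or 22 per arm (4.8% of 922). The allowance matches patients who do not contribute to the primary test.

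**2. Put the drop-outs back.** Pearson chi-square without continuity correction, equal to z² with z = (p₁ − p₂)/√(2·p̄(1 − p̄)/n). The documents give neither the split of drop-outs by arm nor their event rates. The 22 per arm and all event counts among them are therefore assumptions.

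Example, 88/461 versus 66/461: difference 22/461 = 0.0477; p̄ = 154/922 = 0.1670; standard error 0.0246; z = 1.94; p = 0.052.

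| Result without drop-outs | Events restored, standard/deep | Table with 461 per arm | p |
|---|---|---|---|
| Borderline: 88/439 v 64/439, p=0.032 | 4/4 | 92 v 68 | 0.037 |
| | 0/2 | 88 v 66 | 0.052 |
| | 4/8 | 92 v 72 | 0.085 |
| | 8/4 | 96 v 68 | 0.016 |
| Planned: 88/439 v 53/439, p=0.001 | 4/8 | 92 v 61 | 0.006 |
| | 0/11 | 88 v 64 | 0.033 |
| | 0/13 | 88 v 66 | 0.052 |

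The borderline result was chosen to lie near 0.05 and is not a design figure. For the planned effect to cross 0.05, 13 of 22 deep-arm drop-outs (59%) and none of the standard-arm drop-outs must have events.

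**3. What drives the bias.** Take no true effect, 20% events in both arms, and the extreme case that every drop-out would have had an event. A 22/22 split leaves the type I error at 5%. With 11 standard and 33 deep, the observed rates are (92.2 − 11)/450 = 18.0% and (92.2 − 33)/428 = 13.8%, and the test rejects about 40% of the time. The risk comes from unbalanced drop-out related to outcome. Losing 44 patients does not by itself create it.

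**4. Power if everyone is kept.** Power = Φ[(|p₁ − p₂| − 1.960·SE₀)/SE₁], with SE₀ pooled and SE₁ unpooled. There are 461 per arm: 439 at 20% versus 12%, plus 22 drop-outs at assumed rates.

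| Drop-out event rate, standard/deep | Arm rates | Power |
|---|---|---|
| 20%/12% (design) | 20.0% v 12.0% | 91.3% |
| 20%/20% | 20.0% v 12.4% | 88.2% |
| 20%/30% | 20.0% v 12.9% | 83.4% |

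**The case against.** The exclusions are listed in advance, and the endpoint is "Incidence of intra-operative adverse events during laparoscopic surgery". A patient who never has a laparoscopic procedure fits that definition poorly, so a set omitting such patients could be defended if prespecified and justified. The surgeon and attending anaesthesiologist are described as blinded, with a saline pump as dummy, and no section gives the unblinded researcher the withdrawal decision. The threatening p-values come from a constructed borderline result, while the planned effect is hard to overturn. All of this stands, and it limits the weight of the point. It does not supply the missing analysis set or outcome rule. Nor does blinding settle early conversion, because block depth may itself affect the surgical field.

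The wording in 8.6 is also not conclusive. It could mean that these patients count as having no event. The inflation to 922 points to exclusion, but neither 8.6 nor 10.1 says so. If the other meaning was intended, the text still needs correcting.

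A reader might infer that induction drop-out is the main problem and early conversion a minor one. The documents do not support that ranking. Both criteria are open-ended, and early conversion happens during the operation under the allocated block.

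**Conclusion.** The point holds and should be fixed. On the most natural reading of 4.4 and 8.6, the primary test omits about 44 of 922 patients after randomisation and is not intention-to-treat. Early conversion and induction safety events both deserve attention, and the documents give no ground for putting one first.

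A reader might go further and infer that the result will be biased, or biased in favour of deep block. The documents do not show this. They contain no drop-out split and no event rates, so size and direction are unknown, and bias is nil if exclusions are balanced and carry equal risk. On the assumed 22 per arm, an excess of two deep-arm events is enough to move a borderline result past 0.05. The planned effect changes only with a very unbalanced 0/13.

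**What to change.** Change 4.4, 8.6 and 10.1, and add a line in 8.3 on the scoring window:

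1. Define the primary set as all randomised patients who started the allocated neuromuscular regimen, analysed in their allocated arm. Do not remove patients from it for early conversion or for safety events at induction. This concerns the analysis only; clinical withdrawal is unaffected. Score CLASSIC up to conversion or abandonment. State whether the CLASSIC window includes induction and, if it does not, report induction events by arm separately.
2. Because starting the regimen is itself a post-randomisation condition, add a sensitivity analysis of all 922 randomised patients, with a stated outcome rule for those without a scored procedure. Keep the present exclusion set as a further sensitivity analysis.
3. Report drop-outs by arm and reason, and have any exclusion decided by a person blinded to arm.

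The cost is wording, CLASSIC scoring of up to about 44 more patients, and a slight dilution of the effect. If induction is counted, the endpoint widens slightly, and 4.4 does not show that its 20% rate includes such events. Restate the power for the chosen set, using the range in the working (91.3% to 83.4% with 461 per arm under the assumed rates). No added enrolment is needed.
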